6.2.2 Exclusion Criteria

Individuals who meet any of the following exclusion criteria will not be eligible to participate in the study:

1. Diagnosis of squamous or undifferentiated gastric cancer
2. Individuals with inaccessible tumors or for whom biopsy is contraindicated
3. Participated in any other study in which receipt of an investigational new drug or investigational device occurred within 28 days of first dose of study drug
4. Diagnosis of immunodeficiency, receiving TNF pathway inhibitors, PI3 kinase inhibitors, chronic systemic steroid therapy (> 10 mg/day of prednisone or equivalent) or any other form of immunosuppressive therapy within 7 days prior to the first dose of study drug
5. Clinical evidence of ascites by physical exam

6. Prior anti-cancer monoclonal antibody within 4 weeks prior to first dose of study drug or has not recovered from adverse effects due to agents administered more than 4 weeks earlier
7. Prior chemotherapy, targeted small molecule therapy, or radiation therapy within 2 weeks prior to first dose of study drug, or has not recovered from adverse effects (i.e. \leq Grade 1 or baseline) from adverse effects due to a previously-administered agent

Note: Subjects with \leq Grade 2 neuropathy or \leq Grade 2 alopecia are an exception to this criterion.

8. Active second malignancy with the exception of any of the following:
 - Adequately treated basal cell carcinoma
 - Squamous cell carcinoma of the skin, or *in situ* cervical cancer
 - Low-risk prostate cancer (i.e. Gleason score < 7 and prostate specific antigen < 10 ng/mL); or
 - Any other cancer from which the individual has been disease-free for ≥ 3 years
9. Received transfusion of blood products (including platelets or red blood cells) or administration of colony stimulating factors (including G-CSF, GM-CSF or recombinant erythropoietin) within 4 weeks prior to first dose of study drug.
10. Active infection requiring systemic therapy
11. Known **active** central nervous system metastases and/or carcinomatous meningitis. Subjects with previously treated brain metastases may participate provided they are stable (without evidence of progression by imaging at least 4 weeks prior to the first dose of study drug and neurologic symptoms have returned to baseline), have no evidence of new or enlarging brain metastases, and are not using steroids for at least 7 days prior to first dose of study drug. This exception does not include carcinomatous meningitis which is excluded regardless of clinical stability.
12. History of (non-infectious) pneumonitis that required steroids, or current pneumonitis
13. History of interstitial lung disease
14. Prior therapy with an anti-PD-1, anti-PD-L1, or anti-PD-L2 agent, or agents targeting other checkpoint pathways (e.g. CTLA-4, LAG-3, GITR, OX40), or prior participation in Merck MK-3475 clinical trials
15. Prior immunotherapy with CRS-207 or any other *Listeria*-based agent, therapeutic cancer vaccine, or adoptive T cell immunotherapy
16. Major surgery or significant traumatic injury occurring within 28 days prior to first dose of study drug

Note: If major surgery occurred > 28 days prior to first dose of study drug, individual must have recovered adequately from the toxicity and/or complications from the intervention prior to first dose of study drug
17. Previous treatment with >2 systemic chemotherapy regimens for advanced disease
18. Known allergy to both penicillin and sulfa antibiotics

19. Unable or unwilling to withhold or discontinue any prohibited or restricted medications/procedures/immunizations for the specified windows during the study
20. If WOCBP, pregnant or breastfeeding; negative pregnancy status must be confirmed within 24 hours of first dose of study drug
21. Known valvular heart disease that requires antibiotic prophylaxis for prevention of endocarditis
22. Clinically significant heart disease (such as uncontrolled angina, myocardial infarction within 3 months of study initiation, congestive heart failure, or New York Heart Association Class III or IV heart failure)
23. History of autoimmune disease that has required systemic treatment in the past 2 years, including:
 - Inflammatory bowel disease (including ulcerative colitis and Crohn's Disease)
 - Rheumatoid arthritis
 - Systemic progressive sclerosis (scleroderma)
 - Systemic lupus erythematosus
 - Autoimmune vasculitis (e.g. Wegener's granulomatosis)
 - Central nervous system or motor neuropathy considered of autoimmune origin (e.g. Guillain-Barre syndrome, myasthenia gravis, multiple sclerosis)

Note: Individuals with vitiligo, Sjogren's syndrome, interstitial cystitis, Graves' or Hashimoto's Disease, celiac disease, diabetes mellitus type 1, or hypothyroidism stable on hormone replacement will be allowed with Medical Monitor approval.

24. Intercurrent illness that is either life-threatening or of clinical significance such that it might limit compliance with study requirements or in the Investigator's assessment would place the subject at an unacceptable risk for study participation;
25. Received a diagnosis of human immunodeficiency virus (HIV)
26. Received a diagnosis of hepatitis B, or hepatitis C for which there is no clear evidence of natural immunity, immunity subsequent to vaccination, or successful eradication of the virus following antiviral therapy (individuals who are hepatitis C antibody positive may be enrolled if negative viral load confirmed at screening)
27. Subjects who have implanted medical devices that pose high risks for colonization and cannot be easily removed (e.g., artificial heart valves, pacemakers, prosthetic joints, orthopedic screw(s), metal plate(s)) if infection occurs. Other common devices such as venous access devices (e.g., Port-a-Cath or Mediport) may be permitted as well as arterial and venous stents and dental and breast implants that were placed more than 3 months prior to first dose of study drug.
28. Prior severe hypersensitivity (\geq Grade 3) to CRS-207, pembrolizumab, or any study drug excipients (e.g. yeast, glycerol)
29. Unhealed wound
30. History or evidence of inherited bleeding diathesis or coagulopathy

31. Received any prophylactic vaccine within 14 days of first dose of study drug or received a live vaccine within 30 days of planned start of study therapy. Seasonal flu vaccines that do not contain a live virus are permitted.

6.2.3 Dosing Eligibility and Delayed Dosing

Subjects must have adequate organ function confirmed (as defined by the laboratory values in Table 6-1) prior to each dosing cycle where CRS-207 is administered; laboratory tests may be performed up to 3 days before dosing.

Table 6-1 Dosing-Eligibility Requirements

Hematologic	Renal	Hepatic
WBC \geq 3000/ μ L	Creatinine \leq 1.5 \times ULN	AST/ALT \leq 5 \times ULN
ANC \geq 1000/ μ L		Bilirubin \leq 1.5 \times ULN OR \leq 3 \times ULN if due to Gilbert's disease
Platelets \geq 90,000/ μ L		
Hemoglobin \geq 8 g/dL		

ALT = alanine aminotransferase; ANC = absolute neutrophil count; AST = aspartate aminotransferase; ULN = institutional upper limit of normal; WBC = white blood cell

Subjects who do not meet dosing eligibility requirements will be monitored; dosing may be delayed up to 2 weeks, after which time it will be considered missed and the subject would continue onto the next scheduled dose. If a dose is delayed more than 2 weeks, contact the Medical Monitor for further instruction on continued dosing.

Pembrolizumab may be administered up to 3 days before or after the scheduled Day 1 of each cycle due to administrative reasons. If subjects on same-day dosing schedule experience severe infusion-related reactions related to the pembrolizumab infusion, the CRS-207 infusion may be delayed to Day 2. CRS-207 must be administered one day after pembrolizumab administration. If the subject experiences a new AE or is recovering from an AE, CRS-207 administration may be delayed up to 7 days and the Sponsor must be notified. If a dose of CRS-207 is delayed beyond 7 days of pembrolizumab, the dose of CRS-207 should be withheld until the next cycle.

Dosing interruptions are permitted in the case of medical / surgical events or logistical reasons not related to study therapy (e.g. elective surgery, unrelated medical events, vacation, and/or holidays). Subjects should be placed back on study therapy within 3 weeks of the scheduled interruption, unless otherwise discussed with the Sponsor. The reason for interruption should be documented in the Subject's study record.

6.2.4 Subject Discontinuation

Subjects will be encouraged to complete the study; however, they may voluntarily withdraw from treatment or the study at any time. The Investigator will provide a written explanation describing the reason for discontinuation from treatment or study in a source document, which will be entered into the electronic case report form (eCRF). Subjects who discontinue treatment

will complete the EOT assessments, [REDACTED] and post-treatment monitoring for CRS-207. Subjects will be encouraged to participate in the Follow-up Period. In the case of subjects lost to follow-up, attempts to contact the subject must be made and documented in the subject's study records. Sites will attempt to obtain vital status data from public records or other external sources where possible if a subject withdraws consent from study (i.e. refuse follow-up for vital status) or is lost to follow up.

A subject in this clinical study may be discontinued from treatment for any of the following reasons:

- The subject withdraws consent or requests discontinuation for any reason
- Occurrence of any medical condition or circumstance that exposes the subject to substantial risk and/or does not allow the subject to adhere to the requirements of the protocol
- Any serious adverse event (SAE), clinically significant AE, severe laboratory abnormality, intercurrent illness, or other medical condition which indicates to the Investigator that continued participation is not in the best interest of the subject
- Pregnancy
- Subject failure to comply with protocol requirements or study-related procedures
- Termination of the study by the Sponsor or the regulatory authority

Subjects who experience an unacceptable toxicity directly attributable to either pembrolizumab or CRS-207 may continue on study and receive either pembrolizumab or CRS-207 as single agent treatment following completion of the Sponsor Consultation Form and approval by the Medical Monitor. Alternatively, study drug administration may revert back to consecutive day-dosing regimen as performed in Cycle 1.

6.2.4.1 Stopping Rules

Subjects will be monitored throughout the study for unacceptable toxicity ([Section 6.3.1.1](#)); provisions are in place for a Safety Run-in, CRS-207 dose reductions, dose modifications, and continuation on either CRS-207 or pembrolizumab as a single agent. The following safety rules will apply to the study to further mitigate potential risk to subjects:

- Grade 5 toxicity (death) in any subject within 30 days of receipt of study drug(s) unless clearly related to an alternative cause other than study drug
- Unacceptable toxicity occurring in >33% of subjects dosed with CRS-207/pembrolizumab

Should these events occur the SRT will evaluate available data within 72 hours of notification of the event(s) and recommend whether to stop the study, suspend dosing and/or enrollment, or determine whether additional dose adjustments are warranted.

6.3 Study Treatments and Additional Medications

Subjects will receive the assigned treatment course described in Table 6-2.

Table 6-2 ADU-CL-14 Study Treatment Course

Study Drug	Dose / Route	Treatment Course
Pembrolizumab	200 mg administered IV over 30 min (-5 min/+10 min)	Day 1 of each cycle
CRS-207	1×10^9 CFU administered IV over ~ 1 hour	Day 2 of Cycle 1 Day 1 of Cycle 2, 3, 4; Q6W thereafter ¹

CFU = colony-forming unit; IV = intravenous; Q6W = every 6 weeks

¹ Subjects who experience tolerability issues may continue to follow the consecutive-day dosing regimen as in Cycle 1 and follow the Schedule of Events for Consecutive Day Dosing ([Table 1-2](#)).

6.3.1 Safety Run-In Period

A Safety Run-in will be completed since there are no precedent data on the use of pembrolizumab with CRS-207. Subjects will be monitored for unacceptable toxicity during the first 28 days (through 7 days after the Cycle 2 dose). During the Safety Run-in, evaluable subjects are defined as those who remain on study for the 28-day monitoring period, subjects with unacceptable toxicity, and subjects who are discontinued for safety reasons at the Investigator's discretion (even if criteria for unacceptable criteria are not met). Treatment of the first 6 subjects that are followed for the 28-day period will be staggered with no more than 1 subject treated per week. In the event that 4 in up to 12 safety-evaluable subjects experience an unacceptable toxicity, the subsequent cohort of 12 subjects enrolled will be administered CRS-207 at a dose reduced by a half-log (dose level -1). In the event of 4 subjects in up to the next 12 safety-evaluable subjects enrolled experience an unacceptable toxicity, the subsequent cohort of 12 subjects enrolled will be administered a reduced dose of CRS-207 (dose level -2). For each dose reduction (to a minimum of 1×10^8 CFU) the first 12 subjects will be treated and unacceptable toxicities assessed as described above. No adjustments will be made to the pembrolizumab dose. The dose levels and dose reduction permutations are provided in Table 6-3.

Table 6-3 Safety Run-in Dose Levels and Dose Reduction Plan

Dose level	Pembrolizumab	CRS-207
1	200 mg	1×10^9 CFU
-1	200 mg	3×10^8 CFU
-2	200 mg	1×10^8 CFU

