A Safety Run-in will be completed since there are no precedent data on the use of pembrolizumab with CRS-207. Subjects will be monitored for unacceptable toxicity during the first 28 days (through 7 days after the Cycle 2 dose). During the Safety Run-in, evaluable subjects are defined as those who remain on study for the 28-day monitoring period, subjects with unacceptable toxicity, and subjects who are discontinued for safety reasons at the Investigator's discretion (even if criteria for unacceptable criteria are not met). Treatment of the first 6 subjects that are followed for the 28-day period will be staggered with no more than 1 subject treated per week. In the event that 4 in up to 12 safety-evaluable subjects experience an unacceptable toxicity, the subsequent cohort of 12 subjects enrolled will be administered CRS-207 at a dose reduced by a half-log (dose level -1; [Table 6-3](#)). In the event of 4 subjects in up to the next 12 safety-evaluable subjects enrolled experience an unacceptable toxicity, the subsequent cohort of 12 subjects enrolled will be administered a reduced dose of CRS-207 (dose level -2; [Table 6-3](#)). For each dose reduction (to a minimum of 1×10^8 CFU) the first 12 subjects will be treated and unacceptable toxicities assessed as described above. No adjustments will be made to the pembrolizumab dose.

Safety data and all unacceptable toxicities will be reviewed by a Safety Review Team (SRT) comprised of participating investigators in the study, the Medical Monitor, and Sponsor

representatives. Once the Safety Run-in is complete, safety will continue to be evaluated on an ongoing basis in this open-label study. Cumulative clinical experience with CRS-207 and pembrolizumab will be used to assess whether AEs are considered expected.

The Schedule of Events is provided in [Table 1-1](#). Subjects who experience tolerability issues with same-day dosing may continue to follow the consecutive-day dosing regimen as in Cycle 1 with Day 1 pembrolizumab followed by Day 2 CRS-207 dosing ([Table 1-2](#)).

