6.5.4 Analysis Sets

Evaluable Analysis Set (EAS) is defined as all subjects who received at least 1 dose of CRS-207 and have at least one evaluable post-baseline RECIST tumor response assessment or were discontinued due to toxicity. The EAS will be the primary population for analyses of tumor-related endpoints (ORR, DCR, DOR, and PFS).

Full Analysis Set (FAS) is defined as all subjects who received at least 1 dose of CRS-207. The FAS will be used for analyses of OS, immunogenicity and other biomarker data, and sensitivity analysis of select tumor-related endpoints.

Safety Set (SAF) includes all subjects who received any study treatment (pembrolizumab or CRS-207). The SAF will be used for all analyses of safety data and may be used for select biomarker data.

Additional analysis sets (e.g. per protocol set) may be defined in the SAP.

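### Run-in evaluability rests on 28 days on study with no required CRS-207 or Cycle 2 dose, so under-exposed subjects can fill places in the 4-of-12 rule as non-events

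*Protocol*

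**What the plan says.** Protocol 6.3.1 sets the run-in window: "Subjects will be monitored for unacceptable toxicity during the first 28 days (through 7 days after the Cycle 2 dose". It then defines who counts: "evaluable subjects are defined as those who remain on study for the 28-day monitoring period", those with an unacceptable toxicity, and "subjects who are discontinued for safety reasons at the Investigator's discretion (even if criteria for unacceptable criteria are not met". The same definition stands in the synopsis, in 6.1 and in SAP 3.1. The trigger for moving the next cohort of 12 to a lower CRS-207 dose level is "In the event that 4 in up to 12 safety-evaluable subjects experience an unacceptable toxicity". No replacement rule is given.

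Section 6.2.3 governs delays. If an adverse event (AE) pushes CRS-207 more than 7 days past pembrolizumab, "the dose of CRS-207 should be withheld until the next cycle". Interruptions for unrelated medical or logistical reasons are also permitted.

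Three criteria turn some under-exposure into an event. Section 6.3.1.1 counts a drug-related delay of more than 8 days in starting Cycle 2, and systemic steroids given for an immune-mediated reaction. Section 6.3.5.2 adds withholding of pembrolizumab during the run-in. Section 6.2.4.1 separately sends the study to SRT review for "Unacceptable toxicity occurring in >33% of subjects dosed with CRS-207/pembrolizumab".

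Elsewhere the protocol does set an exposure condition: in 6.5.4 both the Full Analysis Set and the Evaluable Analysis Set require at least one CRS-207 dose.

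**The concern.** The run-in exists because no data were available on giving these two drugs together. Its denominator should therefore consist of subjects who were exposed to the combination and had the chance to show toxicity. As written, time on study stands in for exposure.

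Cycle 2 matters because, under Table 6-2, it is where same-day dosing first occurs. A subject who has no Cycle 2 dose inside the window, or who skipped CRS-207, says little about that regimen but still takes one of the 12 places as a non-event. A subject discontinued for safety without meeting a listed criterion is also evaluable and not an event.

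At stake are the sensitivity of the 4-of-12 rule and the meaning of any statement that the combination passed its run-in.

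**Working it through.** **What the documents give.** The trigger is 4 events in up to 12. No target toxicity rate and no trigger probability is stated, so there is no plan figure to reproduce. The one internal check is 4/12 = 33.3%, just above the 33% limit in 6.2.4.1.

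**Step 1, timing.** With 3-week cycles, Cycle 2 Day 1 is study Day 1 + 21 = Day 22. Seven further days reach Day 29, which is 28 days after Day 1, so the two descriptions of the window agree when dosing is on time. With a delay of d days, the follow-up after the Cycle 2 dose that falls inside the window is 28 − (21 + d) = 7 − d days.
- d = 3 (the visit window in Table 1-1): 4 days remain.
- d = 7: Cycle 2 falls on Day 29 and 0 days remain.
- d = 8: Cycle 2 falls on Day 30, after the window has closed.

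A drug-related delay of 7 or 8 days is still not an event, because 6.3.1.1 requires more than 8.

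**Step 2, what the event criteria leave uncovered.** Set against 6.2.3, the criteria in 6.3.1.1 and 6.3.5.2 do not reach (a) omission of CRS-207 alone, (b) Cycle 2 delays of 8 days or less, or (c) doses missed for reasons that are not drug-related. Withholding pembrolizumab is an event. No matching statement exists for CRS-207, the only agent whose dose the run-in can change.

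**Step 3, effect on the trigger.** Assumptions, none from the documents: true rate p in fully exposed subjects is 40% or 33%; m of the 12 are under-exposed; their rate q is 0 or p/2. Then

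P(trigger) = Σ over i + j ≥ 4 of C(12−m, i) p^i (1−p)^(12−m−i) × C(m, j) q^j (1−q)^(m−j).

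Stopping at the fourth event does not change this probability.

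Example, p = 0.40, m = 0: P(at most 3) = 0.0022 + 0.0174 + 0.0639 + 0.1419 = 0.2253, so P(trigger) = 0.775.

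Example, p = 0.40, m = 3, q = 0 (nine informative subjects): P(at most 3) = 0.0101 + 0.0605 + 0.1612 + 0.2508 = 0.4826, so P(trigger) = 0.517.

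| Under-exposed of 12 | p = 40%, q = 0 | p = 40%, q = p/2 | p = 33%, q = 0 | p = 33%, q = p/2 |
|---|---|---|---|---|
| 0 | 0.775 | 0.775 | 0.597 | 0.597 |
| 1 | 0.704 | 0.739 | 0.518 | 0.558 |
| 2 | 0.618 | 0.700 | 0.432 | 0.516 |
| 3 | 0.517 | 0.657 | 0.342 | 0.473 |
| 4 | 0.406 | 0.611 | 0.252 | 0.430 |

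At 33%, each zero-risk subject costs about 8 to 9 percentage points and each half-risk subject about 4.

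**Step 4, safety discontinuations.** Three unacceptable toxicities plus three safety discontinuations that meet no listed criterion give a count of 3 of 12, and the rule does not trigger.

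**The case against.** The strongest reply is that the plan already guards against much of this. The delay, steroid and pembrolizumab-withholding criteria convert a good part of toxicity-driven under-exposure into events. The SRT sees all safety data, so a run of safety discontinuations would reach it, and the 33% rule uses dosed subjects as its denominator. This stands and narrows the gap to the three routes in Step 2. It does not repair the count: SRT review under the 33% rule uses the same event list and leads to a recommendation, not to a set reduction.

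It can also be said that the parenthesis about Cycle 2 implies a Cycle 2 dose. That is a fair reading, but the evaluability sentence is tied to remaining on study, and the two readings give different denominators.

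The zero-risk column is near worst case. A subject who misses only the Cycle 2 CRS-207 dose has already received both drugs once, so the half-risk column is the more credible one for that subject.

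A reader might infer more than the text supports:
- *The rule errs only towards keeping the dose.* It does not. A toxicity counts whatever the exposure, so a pembrolizumab-only immune reaction treated with steroids counts towards reducing CRS-207. Subjects who leave early for non-safety reasons drop out while early toxicities stay in.
- *The 4-of-12 count is the only route to a cohort-level reduction.* It is the only automatic one; 6.2.4.1 lets the SRT consider dose adjustments.
- *Pembrolizumab goes ahead when laboratory values fail.* Section 6.2.3 says only that dosing may be delayed. The AE provision is the one that clearly separates the two drugs.
- *The analysis-set definitions show that pembrolizumab-only subjects were in the run-in.* They allow for such subjects but do not show that any stayed 28 days.

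**Conclusion.** The point holds as a gap in the counting definition. Followed as written, 6.3.1 can score a subject with no Cycle 2 exposure in the window, or with CRS-207 omitted for a cycle, as a toxicity-free member of the 12. To the extent that such a subject carries less risk than a fully exposed one, the chance of a trigger falls.

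The size depends on assumed rates and on an assumed number of under-exposed subjects. With one to three such subjects at zero to half risk, the trigger probability moves from 0.775 to between 0.52 and 0.74 at a 40% true rate, and from 0.60 to between 0.34 and 0.56 at 33%. With none, nothing changes. The documents do not show that any run-in subject was under-exposed or that a reduction was missed.

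The fixed 28 days, the description reaching 7 days past the Cycle 2 dose, and the criterion of more than 8 days cannot all hold together when Cycle 2 is late, and must be reconciled.

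**What to change.** In 6.3.1, with matching text in the synopsis, 6.1 and SAP 3.1:
1. Count a subject without unacceptable toxicity as evaluable only if both agents were received in Cycles 1 and 2 and the subject was observed through 7 days after the Cycle 2 dose.
2. Replace subjects who fall short for reasons other than toxicity with the next enrolled from the planned 79.
3. Have the SRT classify AE-driven CRS-207 omissions and safety discontinuations, so that they are not toxicity-free by default.
4. Reconcile the fixed 28 days with the Cycle 2 description and the delay criterion. Whether a shorter delay should itself be an event is a clinical matter on which this point takes no view.

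No dose and no dose-reduction threshold is changed. The cost is a wording amendment and possibly a longer run-in, with no added subjects.

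SAP 3.5 records that development of CRS-207 stopped and that every subject had completed the end-of-treatment visit by 31 January 2018, so the amendment can no longer operate in this trial. The equivalent now is a short table or listing of Cycle 1 and Cycle 2 exposure to each agent for every run-in subject, with the count of unacceptable toxicities among those fully exposed. SAP 10.1 places unacceptable toxicities only in the AE listing, without a run-in denominator. The administration listings already planned should supply the exposure data, so the added work is small.
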